#### **7.6.6.1 Management While on Oral Test Article**

While the subject is receiving po therapy, the investigator will assess the subject daily and choose one of the following outcomes based on the overall clinical response of the subject:

- Continue po test article
- Discontinue test article – this decision will prompt the EOT evaluation (even if the subject does not complete the minimum of 7 days of dosing)

At all times during the study the decision to continue or discontinue test article is made based on the clinical judgment of the investigator. Each daily decision is to be recorded on source documents and the information transferred to eCRFs by blinded study site personnel.

Omadacycline  
PTK0796-AP-17202-Version 1.0; 26Mar2018

Paratek Pharma, LLC.  
IND # 75,928 IND # 73,431

**Table 2. Dosing Blinded iv and Oral Double-Blind, Double-Dummy Design**

Dosing		Group 1 omadacycline	Group 2 omadacycline	Group 3 omadacycline	Group 4 omadacycline	Group 5 Levofloxacin
Day 1		omadacycline 200 mg iv in 150 mL NS	omadacycline 200 mg iv in 150 mL NS	omadacycline 200 mg iv in 150 mL NS	omadacycline 200 mg iv in 150 mL NS	levofloxacin 750 mg iv in 150 mL saline
Days 2 to 7-10 a, b, c	continue iv	omadacycline 200 mg iv in 150 mL NS	omadacycline 100 mg iv in 150 mL NS	omadacycline 100 mg iv in 150 mL NS	omadacycline 100 mg iv in 150 mL NS	levofloxacin 750 mg iv in 150 mL saline
	switch to po b	omadacycline 200 mg iv in 150 mL NS and three placebo tablets resembling omadacycline and three over- encapsulated placebo tablets resembling levofloxacin	omadacycline 100 mg iv in 150 mL NS and three placebo tablets resembling omadacycline and three over- encapsulated placebo tablets resembling levofloxacin	150 mL NS and two 150 mg omadacycline tablets, one placebo tablet resembling omadacycline, and three over- encapsulated placebo tablets resembling levofloxacin	150 mL NS and three 150 mg omadacycline tablets and three over- encapsulated placebo tablets resembling levofloxacin	150 mL NS and three placebo tablets resembling omadacycline and three over- encapsulated 250 mg levofloxacin tablets

Dosing in all treatment groups is once-per-day.

All iv doses will be administered as continuous infusions over 90 minutes.

All oral doses will be taken in a fasted state (no food, antacids or multivitamins containing multivalent cations [eg, aluminum, magnesium, calcium, bismuth, iron, or zinc] or drink except water for at least 6 hours prior to dosing; after dosing, no food for 2 hours, no dairy products, antacids or multivitamins containing multivalent cations for 4 hours).

iv = intravenous, NS = normal saline, po = per oral.

a The total duration of treatment is 7-10 days, Subjects with bacteremia can continue treatment for up to 14 days.

b Starting on Day 2, per investigator's discretion, subjects may be switched to oral dosing per oral switch criteria.

c All therapy may be discontinued after the seventh day of treatment, when the infection is considered clinically cured (based on normalization of the clinical signs and symptoms of infection and the investigator's clinical assessment that continued systemic antibacterial therapy is no longer needed).

## 7.7 Dose Adjustments and Interruptions of Test Article

No dose adjustments or planned interruptions of test article will be permitted during this study.

## 7.8 Method of Assigning Patients to Treatment Groups

All eligible subjects will be randomized via an IxRS that assigns them to the treatment arm. The site delegate will contact the IxRS after confirming that the subject fulfills all the

inclusion criteria and has none of the exclusion criteria. The IxRS will assign a test article to the subject based on a computer-generated randomization schedule. The randomization will be a blocked randomization sequence as defined in the IxRS specifications and Statistical Analysis Plan (SAP). It is possible that not all treatment arms will be enrolling subjects at the same time. Arms may be dropped based on the Bayesian analysis or initiated based on the Bayesian analysis of the ongoing treatment arms. There will always be at least one omadacycline arm and the levofloxacin arm open. Subjects randomized into the study will be assigned the treatment corresponding to the next available number from the computer-generated randomization schedule. The subject is considered randomized when the IxRS provides the test article assignment, regardless of whether the subject actually receives any medication. As this is an adaptive design trial, any updates to the randomization schedule based upon the Bayesian analysis will be incorporated into the IxRS system.

### **7.8.1 Subject Numbering**

Upon signing the informed consent, the subject will be assigned a unique subject number. Subjects who have been pre-screened, but who do not sign an ICF will not be assigned a subject number. A subject who discontinues participation or is withdrawn before receiving a treatment assignment, and who is re-screened at a later time will be assigned a new subject number and recorded as re-screened. Re-screening is at the discretion of the investigator and in consultation with the medical monitor. The investigator will maintain a subject master list to document every subject who has signed an ICF. A copy of this list should be retained in the investigator's study files.

### **7.9 Dispensing Test Article**

Each study site will be supplied by the sponsor with the investigational product and comparator. The IxRS will instruct the pharmacist or designee as to the appropriate therapy, omadacycline or levofloxacin, to be administered. The unblinded site pharmacist or designee will prepare the test article as instructed. The unblinded pharmacist or designee will provide the blinded nurse administering the infusion with the appropriate solutions for each subject covered to conceal the identity of the test article using materials provided by the sponsor and labeled with blinded administration instructions. The po test article will be supplied to the sites in kits that contain active omadacycline tablets or matched placebo tablets, and active levofloxacin over-encapsulated tablets or matched placebo over-encapsulated tablets resembling levofloxacin. Oral test article supplies are completely blinded. Therefore, oral test article supplies can be transferred from the unblinded study personnel to blinded study personnel for storage, dispensation, and reconciliation. The study coordinator/staff will instruct the subject on the use of po test article. The procedures are detailed in the Pharmacy Manual.

### **7.10 Blinding**

The investigator and sponsor will be blinded to treatment group assignments throughout the study. The sponsor designee (eg, study statistical team, IxRS vendor, etc.) will have a designated randomization administrator who will maintain the randomization codes in accordance with standard operating procedures to ensure the blind is properly maintained,

Omadacycline  
PTK0796-AP-17202-Version 1.0; 26Mar2018

Paratek Pharma, LLC.  
IND # 75,928 IND # 73,431

and that only sponsor personnel who require knowledge of treatment assignments will be unblinded (eg, staff involved in maintaining the randomization codes). The DMC will review safety data and the results from the Bayesian analysis of efficacy. Based on this analysis, modifications may be made to the omadacycline treatment groups.

The investigator and sponsor will be blinded to treatment arm assignments. The iv and po phases of the study will be double-blind.

Because the color of the iv test article infusions and placebo infusions differ, all infusion bags and iv tubing will be covered with materials provided by the sponsor so that subjects and blinded study personnel will not know the identity of the test article being administered. The infusion regimen will follow a blinded design with subjects in each study arm receiving the same infusion volumes with the same administration instructions. Blinded study personnel will administer the infusions and collect, review and enter data regarding the iv infusions (eg, start and stop times) into an eCRF. If gravity administration is not the standard of care then an infusion pump may be used. If an infusion pump is used then an unblinded administrator will be required. Personnel identified as unblinded administrators will not participate in any study procedures other than iv administration of test article and the collection, review and entry of iv related data (eg, start and stop times) into an eCRF.

During the po phase, a double-blind, double-dummy design will be used to ensure the blind is maintained. Subjects on the omadacycline arms may receive active omadacycline tablets and over-encapsulated levofloxacin placebo tablets. Subjects on the levofloxacin arm will receive omadacycline placebo tablets and over-encapsulated active levofloxacin tablets. Infusions will be administered concomitantly along with the po treatment to maintain the overall study blind.

The unblinded source documentation binder containing all descriptions of pharmacy preparations and infusions or distributions of test article and any unblinded subject randomization data should be stored separately, and under lock and key, separate from the documents containing blinded information.

Data that could potentially lead to unblinding will not be accessible to anyone other than the following site personnel:

- unblinded study pharmacist or designee
- unblinded study monitor
- unblinded administrator(s)

Unblinding is only to occur in the case of subject emergencies (see [Section 7.11](#), below) and at the conclusion of the study.

## 7.11 Emergency Unblinding of Treatment Assignment

Emergency unblinding should only be undertaken when it is essential to treat the subject safely and efficaciously. Most often, test article discontinuation and knowledge of the possible treatment assignments are sufficient to treat a study subject who presents with an

emergency condition. It is encouraged for the investigator, when contemplating unblinding, to contact the sponsor or sponsor's designated Medical Monitor or designee to confirm the need to unblind, prior to unblinding (see [Section 2](#) for contact information). However, if required, the investigator can unblind without consulting the Medical Monitor.

Emergency code breaks are performed using the IxRS. When the investigator contacts the system to unblind a subject, he/she must provide the requested subject identifying information and confirm the necessity to unblind the subject. The investigator will then receive details of the drug treatment for the specified subject and a fax or e-mail confirming that the treatment assignment of the subject was unblinded. The system will automatically inform the sponsor's monitor for the site and the sponsor that the code has been broken.

It is the investigator's responsibility to ensure that there is a procedure in place at their site to allow access to the IxRS code break information in case of emergency. The investigator will inform the subject how to contact his/her backup in cases of emergency when he/she is unavailable. The investigator will provide protocol number, test article name if available, subject number, and instructions for contacting the sponsor (or any entity to which it has delegated responsibility for emergency code breaks) to the subject in case emergency unblinding is required at a time when the investigator and backup are unavailable.

All steps outlined above will be followed, including contacting the Medical Monitor as soon as possible and not more than 24 hours afterwards. It will be the responsibility of all study personnel to ensure that, except for the above procedure, investigator blinding is maintained until after study completion.

## 7.12 Prior & Concomitant Therapy

Treatments that have been administered within the 7 days prior to the date of informed consent, or during the Screening phase, will be recorded in the eCRF. The investigator is to instruct the subject to notify the study site about any new medications he/she takes after the start of the test article. All medications and significant non-drug therapies (including physical therapy and blood transfusions) administered after the subject starts treatment with test article must be listed in the eCRF (see [Section 9](#)). In addition, for antibacterial agents and anti-emetics administered, the dose, unit, frequency and route must be entered in the eCRF.

## 7.13 Prohibited Therapy

- All investigational medications or devices used during the 30 days prior to Screening are prohibited.

All of the following therapies are excluded starting from the time of consent through EOT visit:

- Potentially therapeutic antibacterial agents (with potential activity against uropathogens responsible for AP) are prohibited for 72 hours prior to randomization through EOT, with

the exception of cases where a subject is deemed a clinical failure during the course of the study and requires treatment with an additional antibacterial agent

- Subjects will be instructed to avoid taking antacids and multivitamins containing multivalent cations (eg, aluminum, magnesium, calcium, bismuth, iron, or zinc) for 6 hours before and within 4 hours after oral doses

### **7.13.1 Concomitant Medications That May Interact with Levofloxacin**

Use of antiarrhythmic agents of Class IA (eg, quinidine, procainamide) or Class III (eg, amiodarone, Sotalol) is prohibited from the time that informed consent is obtained through EOT.

### **7.14 Permitted Treatments**

All other treatments not specified as prohibited are permitted during the study. Subjects requiring additional or alternative antibacterial therapy for their AP will be judged as Clinical Failures and test article will be discontinued. Further treatment for their infection is at the discretion of the investigator or the subject's health care provider and will be considered as a concomitant medication.

Subjects should be encouraged to contact site personnel before starting any new treatment.

For all treatments received by the subject during the study, relevant information must be recorded on the subject's eCRF.

### **7.15 Treatment Compliance**

Intravenous and oral administration will be managed by study personnel. Compliance and any unresolved discrepancies will be documented in the source document and on the drug inventory record. The test article eCRF should reflect the reconciled dosing information provided by the subject charts.

### **7.16 Packaging and Labeling**

The investigational test article, omadacycline and comparator, levofloxacin, will be packaged by the sponsor and supplied to the investigator. Please refer to the Pharmacy manual for additional information.

### **7.17 Storage and Accountability**

Test article must be received at the study site by a designated person, handled and stored safely and properly, and kept in a secured location to which only the investigator and designated staff have access. Upon receipt, the test article should be stored according to the instructions specified on the drug labels. Storage conditions must be adequately monitored and appropriate temperature logs maintained as source data.

The designated study personnel must maintain an accurate record of the shipment and dispensing of test articles in the study specific medication accountability ledger iv drug

Omadacycline  
PTK0796-AP-17202-Version 1.0; 26Mar2018

Paratek Pharma, LLC.  
IND # 75,928 IND # 73,431

---

accountability will be performed by unblinded personnel. Oral drug accountability can be performed by blinded or unblinded personnel.

### **7.18 Investigational Product Retention at Study Site**

At the conclusion of the study, and as appropriate during the course of the study, with instruction from the sponsor, the designated study personnel will destroy on site as permitted by local site operating procedures, or return all unused test articles, packaging, and drug labels. Destruction/return of all test article will be documented and maintained in the site files.

## 8 STUDY PROCEDURES

Written, signed, and dated informed consent will be obtained before any study-related procedures have been performed. Upon signing the informed consent, the subject will then be assigned a study subject number. Adverse events must be recorded from the time the ICF is signed. Subjects who have been pre-screened on the telephone but who do not sign an ICF will not be assigned a subject number. The investigator will maintain a subject master list to document every subject who has signed an ICF. A copy of this list should be retained in the investigator's study files.

### 8.1 Informed Consent

The investigator will provide for the protection of the subjects by following all applicable regulations. These regulations are available upon request from the sponsor. The ICF must be reviewed by the sponsor and approved by the IRB/IEC/REB.

Before any procedures specified in the protocol are performed, a subject must:

- Be informed of all pertinent aspects of the study and all elements of informed consent
- Be given time to ask questions and time to consider the decision to participate
- Voluntarily agree to participate in the study
- Sign and date an IRB/IEC/REB approved ICF

### 8.2 Subject Demographics/Other Baseline Characteristics

Subject demographic and Baseline characteristic data to be collected on all subjects include: date of birth, gender, and race/ethnicity.

### 8.3 Medical History

The investigator will perform a comprehensive history at the Screening visit. Significant medical history (at any time) and any medical history within the past 6 months including ongoing medical conditions at the time of signing of the ICF will be recorded. In addition, subject history of prior UTI and AP will be captured. Where possible, diagnoses are to be recorded. Any event or change in the subject's condition or health status occurring after signing the ICF will be reported as an AE.

### 8.4 Physical Examination

At Screening, a full physical examination will include the examination of general appearance, skin, neck (including thyroid), eyes, ears, nose, throat, lungs, heart, abdomen, back, lymph nodes, extremities, and vascular and neurological systems. If indicated based on medical history and/or symptoms, rectal, external genitalia, breast, and/or pelvic exams may be performed.

Information for all physical examinations must be included in the source documentation at the study site. Significant and relevant findings that are present prior to the start of test

article must be included in the subject's eCRF. Relevant findings that are present prior to the start of test article must be included in the relevant medical history/current medical conditions screen on the subject's eCRF. Significant findings made after the start of test article which meet the definition of an AE must be recorded on the AE screen of the subject's eCRF.

## 8.5 Vital Signs

Vital signs include blood pressure (BP), heart rate, and body temperature.

- Blood pressure and heart rate should be measured within 30 min before, and approximately ( $\pm$  15 minutes) 1 hour after and 3 hours after the completion of the first dose.

The subject's BP and heart rate should be captured after at least 5 minutes (+ 5 minutes) of rest while in a non-standing position (supine or semi-recumbent, head of bed from 0° to 90°). Subsequent vital sign measurements should be captured in the same non-standing position.

Systolic and diastolic BP will be measured using an automated calibrated device, with an appropriately sized cuff.

Heart rate will be measured using an automated calibrated device, when available. If not available, heart rate will be measured manually.

Temperature will be obtained using an electronic (rapid reading) device whenever possible.

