## 7.4 Dose Selection Rationale

The dosing regimen of omadacycline selected for this study is based on the nonclinical and clinical experience to date, including *in vitro* antibacterial activity, PK characteristics, clinical efficacy in prior studies, and the overall safety and tolerability profile. Key considerations in dose selection are summarized below:

- In PTK0796-SDES-0501, the PK of omadacycline iv were linear over the entire dose range (25 mg to 600 mg) as assessed by area under the concentration time curve (AUC). Therefore, the loading dose given on Day 1 in the pivotal Phase 3 trials, 100 mg iv every 12 hours (q12h), is from an exposure perspective comparable to the 200 mg iv loading dose on Day 1 to be utilized in this study.
- In PTK0796-MDES-0601, 200 mg iv for seven days was safe and well tolerated. Alanine aminotransferase was reported as increased in 26% of subjects however the post-baseline change was approximately 30 IU/L on the last day of infusion. A heart rate model demonstrated that the post-baseline increase in heart rate for a 200 mg dose could be minimized to 15 beats per minute with infusion over 60 minutes.
- In PTK0796-UUTI-15103, omadacycline dosed as 200 mg iv on Day 1 followed by 300 mg po daily for 5 days, 300 mg po q12h on Day 1 followed by 300 mg po daily for 5 days and 450 mg po q12h on Day 1 followed by 450 mg po daily for 5 days demonstrated high urinary concentration on Day 1 and Day 5. For the 200 mg iv load followed by 300 mg daily dosing group, mean urinary concentrations ranged from 22 to 65 µg/mL on Day 1 and 21 to 42 µg/mL on Day 5. For the 300 mg dosing group, mean urinary concentrations ranged from 14 to 20 µg/mL on Day 1 and 17 to 30 µg/mL on Day 5. For the 450 mg dosing group, mean urinary concentrations ranged from 11 to 25 µg/mL on Day 1 and 30 to 48 µg/mL on Day 5.

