### 8.11.1 PK Blood Collection and Processing

Blood samples will be collected and analyzed for omadacycline concentration at the following times:

- Just prior to the dose on Day 3 and just prior to last dose of test article;
- 2 to 3 hours after dose on Day 3 and 2 to 3 hours after last dose of test article.

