### 9.2.3 Day 3 Visit Procedures

The following assessments will be performed:

- mPSAQ
- Concomitant medications
- Laboratory tests (urine):  
Urinalysis via dipstick with optional microscopic exam  
Urine culture
- Laboratory tests (blood):  
Hematology (includes coagulation)  
Chemistry  
Blood culture (as required if bacteremia was confirmed at Screening and has not resolved)

- Vital signs: body temperature, BP, heart rate
- AEs
- PK blood collection
- PK urine collection
- Administration and accountability of test article
- Assessment for po switch

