Assessment of need to continue therapy								X	X	X	X				
Investigator's Assessment of Clinical Response													X	X	X

AE = adverse event, BP = blood pressure, CFU = colony forming unit, ECG = electrocardiogram, eCRF = electronic case report form, EOT = end of treatment, ICF = informed consent form, PK = pharmacokinetics, PTE = post-therapy evaluation, SAE = serious adverse event, UTI = urinary tract infection, WBC = white blood cell.

- a Following the signing of an ICF, all screening evaluations should be completed within the 24 hours prior to randomization. The blood culture sample collection should be completed within 24 hours prior to the first dose of test article.
- b Study Day 1 is the first day of test article administration.
- c A Day 7 and 10 visits should be conducted for subjects with treatment extending beyond 7 or 10 days, unless this visit coincides with the EOT visit.
- d To be conducted on the day of or within the 2 days following the last dose of test article. This evaluation should also be conducted for any prematurely withdrawn subject on the day treatment ends.
- e Written and signed ICF must be obtained before any study-related assessment is performed.
- f Subject assessment of symptoms severity will be collected daily through EOT, at PTE and at Final Follow-up.
- g Treatments that have been administered within the 7 days prior to the date of signing the ICF or during the Screening phase will be recorded in the eCRF. All medications and significant non-drug therapies administered after the first dose of test article must be recorded in the eCRF.
- h A clean-catch, midstream urine sample should be collected and immediately sent to the local microbiology laboratory for microscopic evaluation and culture. Quantitative urine culture by appropriate methods should be performed using a calibrated loop that would identify bacteria at a lower limit of 10^3 CFU/mL. WBC counts should be measured by microscopy from spun or unspun urine or dipstick analysis for leukocyte esterase and nitrites.
- i A full physical examination will be completed at Screening, thereafter only changes from screening assessments should be recorded as AEs in the eCRFs.
- j BP and heart rate should be measured within 30 min before, and approximately (± 15 minutes) 1 hour after and 3 hours after the completion of the doses on Day 1.

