#### Table 3Scheduled Study Visits

Study Day is calculated relative to the first dose of test article (Day 1); there is no Day 0 – the day prior to the first dose of test article is Day -1. If no test article is taken, study day is calculated relative to the date of randomization.

For efficacy outcomes, the data collected at the EOT, PTE and FFU visits, regardless of when these occur will be utilized in the analysis in the ITT and micro-ITT population. The CE and ME populations exclusions due to windowing are outlined in Sections 4.4 and 4.5.

For each safety outcome and UTISA data, analyses will utilize assessments occurring during the scheduled visit windows (provided in Table 3). Thus, if a subject has a visit outside the scheduled visit window, for example, a PTE Visit occurred 20 days after the subject's first investigational product dose, the assessment will not be summarized with the PTE Visit but will be considered an unscheduled assessment. If a subject does not have an assessment at a scheduled visit and an unscheduled assessment was taken within the window for the time point (for example, 21 days ( $\pm$  2 days) after the subject's first day of therapy for PTE), these assessments will be summarized in the by time point analyses. If more than one measurement is

93 Version: 1.0 Status: Approved Approved Date: PTK0796-AP-17202 Statistical Analysis Plan

Omadacycline (PTK 0796)

PTK0796-AP-17202 Statistical Analysis Plan

taken during the visit window, the value taken on the scheduled visit will be utilized or if no scheduled visit was done, the first (earliest) measurement in the visit window will be used. If more than one measurement is taken on the same day, the assessment closest to the start of the dose will be used for on treatment values and the last measurement on the day will be used for post-treatment values. For worst overall post-baseline analyses, all assessments including those obtained from unscheduled visits will be included.

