### 8.6 Vital Signs

Vital signs will include blood pressure (diastolic and systolic) and heart rate and will be collected at Screening, Days 1, Day 3, Day 7, Day 10 and at EOT, PTE and FFU visits. On Day 1, blood pressure and heart rate is recorded within 30 min before, and 1 hour ( $\pm$  15 minutes) after and 3 hours ( $\pm$  15 minutes) after the completion of the first dose.

Body temperature is recorded at all visits.

Additionally, height will be collected at the Screening visit, and body weight will be collected at the Screening, EOT and FFU visits.

Blood pressure (systolic and diastolic) and heart rate will be summarized by time point and treatment group and for the minimum and maximum post-baseline values using descriptive statistics, for both the actual values and the change from baseline. Temperature will be summarized by descriptive statistics including change from baseline) by time point

Figures (line graphs) of observed values for heart rate, systolic and diastolic blood pressure over time will also be provided by treatment group.

Post-baseline vital signs will be defined as CN if they meet 1) the criterion value at the given visit, or 2) meet both the criterion value and the change from baseline criterion listed in Table 11. The incidence of CN vital signs will be summarized by time point and treatment group and will be listed and flagged in by-subject listings. An overall post-baseline incidence of CN values for each vital sign parameter, will also be summarized. A separate listing will be provided of subjects with values for a vital sign noted as CN.

0293 Version: 1.0 Status: Approved Approved Date: PTK0796-AP-17202 Statistical Analysis Plan

Omadacycline (PTK 0796)

Paratek Pharma, LLC

PTK0796-AP-17202 Statistical Analysis Plan

Vital Sign Parameter	Flag	Criterion Value	Change from Baseline
Systolic Blood Pressure	High (CH)	≥ 180	Increase of $\geq 20 \text{ mmHg}$
(mmHg)	Low (CL)	≤ 90	Decrease of ≥ 20 mmHg
Diastolic Blood Pressure	High (CH)	≥ 105	Increase of ≥ 15 mmHg
(mmHg)	Low (CL)	≤ 50	Decrease of $\geq 15 \text{ mmHg}$
	High (CH)	≥ 120	Increase of $\geq 15$ bpm
Heart Rate (bpm)	Low (CL)	≤ 5 0	Decrease of $\geq 15$ bpm

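### No timed post-dose heart rate or blood pressure reading falls on a day when the omadacycline regimens differ, so the regimens can be compared on the cited heart rate effect only insensitively

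*Protocol*

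**What the plan says.** Three places agree that the timed set belongs to Day 1. Protocol 8.5 ties it to the first dose, with readings before dosing and "1 hour after and 3 hours after the completion of the first dose". Footnote j of the Schedule of Events (Protocol Appendix 1) has the post-dose readings "1 hour after and 3 hours after the completion of the doses on Day 1". SAP 8.6 repeats it: "On Day 1, blood pressure and heart rate is recorded within 30 min before, and 1 hour".

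On later treatment days the protocol lists the measurement without a time. The Day 3 entry in Protocol 9.2.3 reads "Vital signs: body temperature, BP, heart rate", and the Day 7 and Day 10 entries (9.2.7, 9.2.9) do the same. SAP 8.6 confirms the days: blood pressure and heart rate "will be collected at Screening, Days 1, Day 3, Day 7, Day 10 and at EOT, PTE and FFU visits".

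The dose rationale in Protocol 7.4 names one cardiovascular effect, a modelled heart rate increase at 200 mg that "could be minimized to 15 beats per minute with infusion over 60 minutes".

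For several readings on one day, SAP 5.4 says that "the assessment closest to the start of the dose will be used for on treatment values". SAP 8.6 summarises heart rate and blood pressure by time point and treatment group. It adds minimum and maximum post-baseline values, clinically notable incidence and line graphs by group.

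**The concern.** Repeated 200 mg iv is what sets Group 1 apart, and the heart rate rise is the only cardiovascular effect that the protocol raises when it justifies the doses. A post-infusion effect is best seen at a fixed time after the infusion. The plan fixes that time only on the day when the four omadacycline arms cannot differ. Afterwards a site may read one subject before the infusion and another hours after it, and that timing variation goes straight into the by-arm figures.

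This matters because safety of omadacycline is a secondary objective, and SAP 3.4 bases re-allocation and dropping of dose groups primarily on safety and tolerability. A weak regimen contrast on heart rate would inform both those decisions and later dose selection.

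**Working it through.** **Step 1. Timed readings against dose.** Doses are from Protocol Table 1. Reading days are from Protocol 9 and SAP 8.6, because the column alignment of the Appendix 1 table is uncertain in the text available to me.

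| Day | Group 1 | Group 2 | Group 3 | Group 4 | Timed post-dose readings |
|---|---|---|---|---|---|
| 1 | 200 mg iv | 200 mg iv | 200 mg iv | 200 mg iv | 2 (1 h, 3 h) |
| 3, 7, and 10 if treated | 200 mg iv | 100 mg iv | 100 mg iv or 300 mg po | 100 mg iv or 450 mg po | 0 |

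The end-of-treatment reading, up to 2 days after the last dose, is also untimed. So the timed readings contain no regimen contrast, and the readings that contain one are untimed.

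**Step 2. What SAP 5.4 does with several readings in a day.** Infusions last 90 minutes. A reading 1 hour after completion is 90 + 60 = 150 minutes, or 2.5 hours, from dose start. Any reading taken less than 2.5 hours before the dose is nearer and displaces it from the by-visit table.

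**Step 3. What the maximum post-baseline value does.** It includes the Day 1 readings at 1 and 3 hours. Whenever a subject's highest value is one of these, the maximum carries no regimen information, which dilutes any difference between omadacycline arms.

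**Step 4. What a timed reading could show (illustration).** The plan states no figure to reproduce here. Inputs:
- 15 bpm at 200 mg (Protocol 7.4).
- Effect proportional to dose: assumption. Difference between 200 and 100 mg = 15 − 7.5 = 7.5 bpm.
- Between-subject SD 12 to 15 bpm: assumption.
- 40 per arm: 200 / 5 under the initial equal allocation. Adaptive re-allocation could change this.

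Group 1 against Group 2, SE = SD × √(1/40 + 1/40) = SD × 0.2236; power ≈ Φ(difference / SE − 1.96).

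| SD (bpm) | SE (bpm) | 7.5 / SE | Power |
|---|---|---|---|
| 12 | 2.7 | 2.8 | 0.80 |
| 15 | 3.4 | 2.2 | 0.61 |

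Protocol 7.4 gives the 15 bpm for a 60-minute infusion, and this trial infuses over 90 minutes, so the difference may be smaller. At 5 bpm the same formula gives power of 0.46 (SD 12) and 0.32 (SD 15).

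**The case against.** The plan does collect heart rate and blood pressure when the regimens differ, on Days 3, 7 and 10 and at end of treatment, and SAP 8.6 reports them by group. A reader might infer from the Day 1 timing that the trial cannot compare its regimens on heart rate. The documents do not support that: the comparison exists and is only less sensitive. The Day 1 readings also have a purpose of their own. They cover the largest iv dose in the trial and compare omadacycline with levofloxacin at fixed times.

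The SAP 5.4 rule acts only if a site takes more than one reading in a day, which Protocol 9 does not ask for. It can also select a reading after dose start. SAP 5.4 keeps every assessment in the worst post-baseline analyses, so a high post-infusion value is not lost from those. All of this stands, subject to the dilution in Step 3.

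Other inferences go too far:
- The 15 bpm change in SAP Table 11 is not a threshold on its own. A high heart rate flag requires at least 120 bpm, so a 15 bpm rise alone never flags.
- Heart rate may fall as fever resolves, but recovery common to the randomised arms does not bias a between-arm contrast on a given day.
- Protocol 7.4 gives no basis for a blood pressure effect. Blood pressure is included here only because it is read at the same time.
- Whether the DMC would miss a difference cannot be judged, because its reports and criteria are in a charter that is not part of these documents.
- Setting Group 1 against Groups 2 to 4 pooled would look more powerful, but it treats Groups 3 and 4 as still on 100 mg iv when they may have switched to tablets.

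It can also be said that an hour after a placebo infusion is not a matched post-dose time for subjects who have switched to oral drug. That is correct and limits what the fix delivers for Groups 3 to 5. It does not affect Group 1 against Group 2, which stay on iv drug throughout.

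**Conclusion.** The point holds in this form. No timed post-dose heart rate or blood pressure reading is specified on any day when the omadacycline regimens differ. The planned by-arm comparison of the effect cited in Protocol 7.4 therefore rests on readings with no set relation to dosing. It is possible but insensitive, and the same-day selection rule and the inclusion of Day 1 in the maximum can weaken it further.

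The timing finding comes directly from the documents and needs no assumption. The size does not: 7.5 bpm, an SD of 12 to 15 bpm and 40 per arm put a timed Group 1 against Group 2 contrast 2.2 to 2.8 standard errors from zero, and a smaller effect under the 90-minute infusion would lower that. The weakness does not invalidate the trial. It gives up sensitivity on a safety contrast that a timing instruction could largely recover.

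**What to change.** 1. In Protocol 8.5, Appendix 1 and SAP 8.6, set the blood pressure and heart rate readings already scheduled on Day 3, Day 7 and, if still on treatment, Day 10 at about 1 hour (±15 minutes) after completion of that day's infusion. Record the time of any oral dose that day.
2. In SAP 5.4 and 8.6, use this timed value, not the one closest to dose start, for the by-arm summaries on those days.
3. In SAP 8.6, report the maximum post-baseline value from Day 2 onward as well as overall.
4. State that Group 1 against Group 2 is the cleanest contrast, and that in switched subjects in Groups 3 to 5 the reading is timed to a placebo infusion and not to the active oral dose.

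Every arm receives a daily infusion, active or placebo (Protocol 7.6.3, Table 2), so the blind is kept. No visit or procedure is added, and infusion start and stop times already go on the eCRF (Protocol 7.6.1). The cost is that staff must take the reading about 1 hour after the infusion ends and note the time, including at approved outpatient centres. On Day 3 they already attend for a PK sample ("2 to 3 hours after dose on Day 3 and 2 to 3 hours after last dose of test article"). If that window runs from infusion start, the reading at 2.5 hours falls inside it. Day 7 has a PK sample only if it is the day of the last dose.
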